### **6.5.2 Clinical Laboratory Evaluations**

Clinical laboratory evaluations (including clinical chemistry panel [should be fasted at least 8 hours], thyroid-stimulating hormone [Screening only], hematology, and urinalysis; [Appendix A](#)) will be collected at the timepoints specified in [Table 6-1](#) and [Table 6-2](#).

Screens for a hepatitis panel and HIV antibody will be performed at Screening. A drug screen for selected drugs of abuse, including cotinine (not including alcohol), will be performed at Screening and repeated (including alcohol) at Check-in.

### **6.5.3 Vital Signs**

Vital signs measurements (including oral temperature, BP, heart rate, and respiratory rate) will be obtained at the timepoints specified in [Table 6-1](#) and [Table 6-2](#). Vital signs will be measured after the subject has been supine for at least 5 minutes.

### **6.5.4 Twelve-lead Electrocardiograms**

A 12-lead ECG will be obtained at the timepoints specified in [Table 6-1](#) and [Table 6-2](#). Subjects will be supine for at least 5 minutes prior to obtaining an ECG measurement.

The ECG parameters (including heart rate; PR, QRS, and QT intervals; and QTcF) and the Investigator's (or designee's) overall interpretation of the ECG will be recorded in the eCRF.

### **6.5.5 Physical Examinations**

Complete physical examinations and abbreviated physical examination (general, heart, lungs, abdomen, and skin) will be performed at the timepoints specified in [Table 6-1](#) and [Table 6-2](#). The time and date of the physical examination will be recorded in the eCRF and any clinically significant findings will be recorded as AEs.

## **7 DATA ANALYSES AND SAMPLE SIZE**

### **7.1 Sample Size**

The sample sizes chosen for Parts 1 and 2 of this study were based on precedent set by other AME and absolute bioavailability studies of similar nature and were not based on power calculations.

### **7.2 Study Populations**

The PK Populations for Parts 1 and 2 will consist of all subjects who received at least 1 dose of study drug and have evaluable PK data.

The Safety Population will consist of all subjects who received at least 1 dose of study drug.

The All Subject Population will consist of any subjects who enrolled on to the study (signed informed consent).

### **7.3 Pharmacokinetic Analysis**

#### **Part 1:**

Whenever possible, the following PK parameters will be calculated for each subject, based on the plasma concentrations of LOXO-292 and the whole blood and plasma concentrations of total radioactivity, according to the model independent approach.

$C_{\max}$	maximum observed concentration
$T_{\max}$	time to maximum observed concentration
$AUC_{\text{last}}$	AUC from time 0 to the time of the last quantifiable concentration, calculated using the linear trapezoidal rule for increasing concentrations and the logarithmic rule for decreasing concentrations
$AUC_{0-\infty}$	AUC extrapolated to infinity, calculated using the formula: $AUC_{0-\infty} = AUC_{\text{last}} + (C_{\text{last}} \div \lambda_z)$

$\lambda_z$	where $C_{last}$ is the last quantifiable concentration and $\lambda_z$ is the apparent terminal elimination rate constant
$t_{1/2}$	apparent terminal elimination rate constant, where $\lambda_z = \ln 2 / t_{1/2}$
CL/F	where $t_{1/2} = \ln 2 / \lambda_z$
V z /F	apparent systemic clearance (for LOXO-292 only)
	apparent volume of distribution during the terminal phase (for LOXO-292 only)

**Blood/Plasma AUC Ratio**

$AUC_{0-\infty}$  of total radioactivity in whole blood/ $AUC_{0-\infty}$  of total radioactivity in plasma

**Plasma LOXO-292 /Total Radioactivity AUC Ratio**

$AUC_{0-\infty}$  of LOXO-292 in plasma/ $AUC_{0-\infty}$  of total radioactivity in plasma.

Additionally, blood-to-plasma ratios at each sampling timepoint will be calculated to determine partitioning of total radioactivity into red blood cells.

In addition, for each subject, the following PK parameters will be calculated whenever possible, based on the urine concentrations of total radioactivity:

A eu	amount excreted in urine per sampling interval
Cum A eu	cumulative amount excreted in urine
%f eu	percentage of dose excreted in urine per sampling interval, where $\%f_{eu} = 100 (A_{eu}/dose)$
Cum %f eu	cumulative percentage of dose excreted in urine.

For each subject, the following PK parameters will be calculated whenever possible, based on the fecal concentrations of total radioactivity:

A ef	amount excreted in feces per sampling interval
Cum A ef	cumulative amount excreted in feces
%f ef	percentage of dose excreted in feces per sampling interval, where $\%f_{ef} = 100 (A_{ef}/dose)$
Cum %f ef	cumulative percentage of dose excreted in feces.

Part 2:

Oral dose PK: Whenever possible, the following PK parameters will be calculated for each subject, based on the plasma concentrations of LOXO-292:

$C_{max}$	maximum observed concentration
$T_{max}$	time to maximum observed concentration
$AUC_{last}$	AUC from time 0 to the time of the last quantifiable concentration
$AUC_{0-\infty}$	AUC extrapolated to infinity, calculated as described above
$\lambda_z$	apparent terminal elimination rate constant
$t_{1/2}$	apparent terminal elimination half-life (whenever possible), where $t_{1/2} = \text{natural log (2)}/\lambda_z$
F	absolute bioavailability, calculated using the formula: $F = \frac{AUC_{0-\infty}(\text{oral}) \times \text{Dose (IV)}}{AUC_{0-\infty}(\text{IV}) \times \text{Dose (oral)}}$
CL/F	apparent systemic clearance
$V_z/F$	apparent volume of distribution during the terminal phase.

Intravenous dose PK: For each subject, the following PK parameters will be calculated whenever possible, based on the plasma concentrations of [C]-LOXO-292:

$C_{max}$	maximum observed concentration
$T_{max}$	time to maximum observed concentration
$AUC_{last}$	AUC from time 0 to the time of the last quantifiable concentration
$AUC_{0-\infty}$	AUC extrapolated to infinity, calculated as described above
$\lambda_z$	apparent terminal elimination rate constant
$t_{1/2}$	apparent terminal elimination half-life (whenever possible), where $t_{1/2} = \text{natural log (2)}/\lambda_z$
CL	systemic clearance
$V_z$	volume of distribution during the terminal phase
$V_{ss}$	volume of distribution at steady state.

In addition, for each subject, the following PK parameters will be calculated whenever possible, based on the urine concentrations of LOXO-292, [C]-LOXO-292, and total radioactivity:

$A_{eu}$	amount excreted in urine per sampling interval
Cum $A_{eu}$	cumulative amount excreted in urine
$CL_R$	renal clearance (LOXO-292 and [  C]-LOXO-292 only), where $CL_R = A_{eu}/AUC$
	$AUC_{0-\infty}$ may be used, if appropriate
$\%f_{eu}$	percentage of dose excreted in urine per sampling interval, where $\%f_{eu} = 100 (A_{eu}/\text{dose})$

Cum %feu cumulative percentage of dose excreted in urine.

Whenever possible, the following PK parameters will be calculated for each subject, based on the fecal concentrations of total radioactivity:

A ef	amount excreted in the feces per sampling interval
Cum A ef	cumulative amount excreted in feces
%f ef	percentage of dose excreted in feces per sampling interval, where %f ef = 100 (A ef /dose)
Cum %f ef	cumulative percentage of dose excreted in feces.

Pharmacokinetic calculations will be performed, if appropriate, using commercial software such as Phoenix™ WinNonlin® Version 6.4 or higher (Certara USA Inc.).

Pharmacokinetic parameters for relevant metabolites of LOXO-292 may be calculated in Part 1 and/or Part 2, as deemed appropriate, based on plasma, urine, and/or fecal concentration levels.

Other parameters may be added as appropriate. Final PK parameters reported will be detailed in the Statistical Analysis Plan (SAP).

Pharmacokinetic analysis will use actual times as recorded on the eCRF. Other data handling procedures will be detailed in the SAP.

#### **7.4 Statistical Analysis of Pharmacokinetic Data**

For Parts 1 and 2, descriptive statistics (number of observations, arithmetic mean, standard deviation, median, minimum, maximum, geometric mean, and geometric coefficient of variation) will be calculated for the PK parameters. No formal statistical analyses are planned.

Specification of PK parameters for analysis; procedures for accounting for missing, unused, or spurious data; procedures for reporting deviations from the original statistical plan; and selection of subjects to be included in the analyses population(s), as applicable, will be presented in the Clinical Study Report and/or SAP as appropriate.

#### **7.5 Statistical Analyses of Safety Data**

For Parts 1 and 2, descriptive statistics will be calculated on the safety parameters. No formal statistical analyses are planned.

All AEs will be coded by the Medical Dictionary for Regulatory Activities (Version 20.0 or higher). Each sign or symptom reported will be graded on the National Institution of Health's

Common Terminology Criteria for Adverse Events Version 5.0 (or higher) toxicity grading scale as referenced in [Appendix C](#). The number (%) of subjects with any AE will be summarized by system organ class and preferred term. Descriptive statistics will be provided for clinical laboratory values, vital signs, and ECGs. Concomitant medications will be listed and coded according to the World Health Organization Drug Dictionary (September 2015 or later). Additional details will be provided in the SAP.

## **7.6 Data Handling and Record Keeping**

Any changes to information in the trial progress notes and other source documents will be initialed and dated on the day the change is made by a CRU staff member authorized to make the change. Changes will be made by striking a single line through erroneous data and clearly entering the correct data (eg, ~~wrong data~~ right data). If the reason for the change is not apparent, a brief explanation for the change will be written adjacent to the change by the clinician.

The Data Management Plan will be approved by the Sponsor.

Data will be validated during data entry by the CRU and verified by the Study Monitor. Data will then be reviewed by the data management group to resolve any outstanding issues. Listings will be generated after the database is cleaned by Data Management and will be reviewed by the Covance scientific team. The eCRF and ancillary data will be converted into final SAS datasets following Study Data Tabulation Model or client-provided specifications. The final datasets structure will be verified using Web Submission Data Manager®, while the dataset content will be peer reviewed by an independent programmer.

The tables, figures, and listings (TFLs) will be programmed per the final SAP. All TFLs will be peer reviewed by an independent programmer. In addition, draft TFLs will be reviewed by the Covance scientific team during the dry run and data review meetings.

The peer review will be performed by independent programmers following the quality control process and programming checklists.

## **7.7 Quality Control and Quality Assurance**

Quality control and quality assurance will be performed according to Covance standard operating procedures or per client request and as applicable according to the contract between Covance and the Sponsor.

## 8 ADMINISTRATIVE ASPECTS

### 8.1 Change in Protocol

There will be no alterations in the protocol without agreement between the Sponsor and the Investigator (or designee).

There will be no alterations in the protocol affecting subject safety without the express written approval of the Sponsor, Investigator (or designee), and the IRB (see Form FDA 1572).

### 8.2 Site Initiation Visit/Investigator Meeting

Prior to the start of the clinical study, the representative(s) of the Sponsor will meet with the Investigator (or designee) and appropriate clinical staff to familiarize the Investigator (or designee) and clinical staff with the materials necessary for conducting the clinical study.

### 8.3 Disclosure

All information provided regarding the study, as well as all information collected/documentated during the study, will be regarded as confidential. The Investigator (or designee) agrees not to disclose such information in any way without prior written permission from the Sponsor.

Any publication of the results, in part or in total (eg, articles in journals or newspapers, oral presentations, abstracts) by the Investigator (or designee) or their representative(s), shall require prior notification and review, within a reasonable timeframe, by the Sponsor, and cannot be made in violation of the Sponsor's confidentiality restrictions or to the detriment of the Sponsor's intellectual property rights.

### 8.4 Monitoring

The Sponsor will designate a Sponsor's Study Monitor who will be responsible for monitoring this clinical trial. The Sponsor's Study Monitor will monitor the study conduct, proper eCRF and source documentation completion and retention, and accurate study drug accountability. To this end, the Sponsor's Study Monitor will visit the CRU at suitable intervals and be in frequent contact through verbal and written communication. It is essential that the Sponsor's Study Monitor has access to all documents (related to the study and the individual participants) at any time these are requested. In turn, the Sponsor's Study Monitor will adhere to all requirements for subject confidentiality as outlined in the ICF. The Investigator (or designee) and Investigator's staff will be expected to cooperate with the Sponsor's Study Monitor, to be available during a portion of the monitoring visit to answer questions, and to provide any missing information.

## **8.5 Institutional Review Board**

In accordance with US Title 21 CFR 56, the protocol, advertisement, ICF, and other information provided to subjects will be reviewed and approved by the IRB. The Sponsor will supply relevant material for the Investigator (or designee) to submit to the IRB for the protocol's review and approval. Verification of the IRB unconditional approval of the protocol and the written ICF statement will be transmitted to the Investigator (or designee).

The IRB will be informed by the Investigator (or designee) of subsequent protocol amendments and of serious and unexpected AEs. Approval for protocol amendments will be transmitted in writing to the Investigator (or designee). If requested, the Investigator (or designee) will permit audits by the IRB and regulatory inspections by providing direct access to source data/documents.

The Investigator (or designee) will provide the IRB with progress reports at appropriate intervals (not to exceed 1 year) and a Study Progress Report following the completion, termination, or discontinuation of the Investigator's (or designee's) participation in the study.

## **8.6 Informed Consent**

Written informed consent for the study will be obtained from all subjects before protocol-specific procedures are carried out. The ICF will be approved (along with the protocol) by the IRB and will be acceptable to the Sponsor.

The Investigator (or designee) will explain the nature of the study and the action of the test product. The subjects will be informed that participation is voluntary and that they can withdraw from the study at any time. In accordance with 21 CFR 50, the informed consent process shall be documented by the use of a written ICF approved by the IRB and signed by the subject prior to protocol-specific procedures being performed.

The subject will sign 2 copies of the ICF. One copy will be given to the subject, and the other will be maintained with the subject's records.

## **8.7 Records**

The results from data collected at Screening and during the study will be recorded in the subject's eCRF. To maintain confidentiality, the subjects will be identified only by numbers.

The completed eCRFs will be transferred to the Sponsor (or designee). Copies of each eCRF will be retained by the Investigator (or designee). All source documents, records, and reports will be retained by the CRU in accordance with 21 CFR 312.62(c).

All primary data, or copies thereof (eg, laboratory records, eCRFs, data sheets, correspondence, photographs, and computer records), which are a result of the original observations and activities of the study and are necessary for the reconstruction and evaluation of any study report, will be retained in the CRU archives.

### **8.8 Reference to Declaration of Helsinki/Basic Principles**

The study procedures outlined in this protocol will be conducted in accordance with the US CFR governing Protection of Human Subjects (21 CFR 50), Financial Disclosure by Clinical Investigators (21 CFR 54), IRBs (21 CFR 56), Investigational New Drug Application (21 CFR 312), Applications for FDA Approval to Market a New Drug (21 CFR 314), and Radioactive Drugs for Certain Research Uses (21 CFR 361.1), as appropriate. As such, these sections of US Title 21 CFR, along with the applicable International Council for Harmonisation Guidelines, are commonly known as Good Clinical Practices, which are consistent with the Declaration of Helsinki.

### **8.9 Financing and Insurance**

Financing and insurance will be addressed in a separate agreement.

## APPENDIX A - CLINICAL LABORATORY EVALUATIONS

Clinical Chemistry Panel (Fasted):	Hematology:	Urinalysis:
Alanine aminotransferase	Hematocrit	Bilirubin
Albumin	Hemoglobin	Color and appearance
Alkaline phosphatase	Mean corpuscular hemoglobin	Glucose
Aspartate aminotransferase	Mean corpuscular hemoglobin concentration	Ketones
Blood urea nitrogen	Mean corpuscular volume	Leukocyte esterase
Calcium	Platelet count	Nitrite
Chloride	Red blood cell (RBC) count	Occult blood
Cholesterol	RBC distribution width	pH and specific gravity
Creatinine	White blood cell (WBC) count	Protein
Glucose	WBC differential (absolute and percent):	Urobilinogen
Iron	Basophils	Microscopic exam including bacteria, casts, crystals, epithelial cells, RBCs, and WBCs (if protein, leukocyte esterase, nitrite, or blood is positive)
Phosphorus	Eosinophils	
Potassium	Lymphocytes	
Sodium	Monocytes	
Thyroid-stimulating hormone (at Screening only)	Neutrophils	
Total bilirubin		
Total protein		
Triglycerides		
Uric acid		
Amylase		
Lipase		

### Drug Screen:

Including but not limited to the following:

Alcohol (ethanol, Day -1 only, by breathalyzer)

Amphetamines/methamphetamines

Barbiturates

Benzodiazepines

Cannabinoids

Cocaine (metabolite)

Cotinine (by urinalysis)

Methadone

Opiates

Phencyclidine

### Serology:

Hepatitis B surface antigen

Hepatitis B core antibody

Hepatitis C virus antibody

Human immunodeficiency virus antibody

## APPENDIX B - BLOOD SAMPLING SUMMARY

Part 1			
Purpose	Maximum Blood Volume per Sample (mL)	Maximum Number of Blood Samples	Maximum Total Volume (mL)
Serology	4	1	4
Hematology	4	4	16
Clinical Chemistry	4	4	16
LOXO-292 and Total Radioactivity Sampling	6	25 a	150
Metabolite Sampling	10	19 a	190
Approximate Total Blood Volume			376

Part 2			
Serology	4	1	4
Hematology	4	4	16
Clinical Chemistry	4	4	16
LOXO-292, [  C]-LOXO-292, and Total Radioactivity Sampling	6	25	150
Approximate Total Blood Volume			186

a Total number of blood samples collected in Part 1 for LOXO-292/total radioactivity analysis and for metabolite profiling/characterization is based on subject confinement until Day 22. If a subject meets the discharge criteria as defined in Table 6-1 earlier than Day 22, the total number of blood samples collected and the total blood volumes will be less.

## APPENDIX C - ADVERSE EVENTS

### 1 ADVERSE EVENTS

#### 1.1 Definition of Adverse Events

An adverse event (AE; or adverse experience) is defined as any untoward medical occurrence experienced by a patient or healthy subject, whether or not considered drug related by the Investigator (or designee). A treatment-emergent AE is an AE that is reported after a dose of study drug.

The following are all AEs:

- Unfavorable changes in general condition;
- Subjective or objective signs/symptoms;
- Concomitant diseases or accidents;
- Clinically relevant adverse changes in laboratory parameters observed in a subject during a clinical study.

Adverse events comprise all disturbances of general health status, subjective and objective disease symptoms (including laboratory abnormalities), and accidents observed in the context of a clinical trial, irrespective of a possible causal relationship with the administration of the trial substance. Events occurring in the framework of a clinical trial during drug-free and post-treatment periods, under placebo, or in a reference group receiving drug or nondrug therapy are also to be designated as AEs. All AEs, complaints, or symptoms that occur from the time informed consent is signed until the Safety Follow-up Call are to be recorded on the appropriate electronic Case Report Form (eCRF) (events that occur prior to consent are considered medical history). Documentation must be supported by an entry in the patient's source medical records. Laboratory test abnormalities considered by the Investigator to be clinically relevant should be reported in the eCRF as an AE. Each AE is to be evaluated for duration, severity, and causal relationship with the investigational product or other factors.

#### 1.2 Categorization of Adverse Events

The severity of AEs will be categorized based on the National Cancer Institute Common Terminology Criteria for Adverse Events (CTCAE) Version 5.0 as follows:

- **Grade 1 Mild:** Asymptomatic or mild symptoms; clinical or diagnostic observations only; intervention not indicated
- **Grade 2 Moderate:** Minimal, local or noninvasive intervention indicated; limiting age-appropriate instrumental Activities of Daily Living (ADL)\*

- **Grade 3 Severe or medically significant but not immediately life threatening:**  
Hospitalization or prolongation of hospitalization indicated; disabling; limiting self-care  
ADL\*\*
- **Grade 4 Life-threatening consequences:** Urgent intervention indicated
- **Grade 5 Death related to AE**

Note: Not all grades are appropriate for all AEs. Therefore, some AEs are listed within the CTCAE with fewer than 5 options for grade selection. Grade 5 (death) is not appropriate for some AEs and therefore is not an option.

\* Instrumental ADL refer to preparing meals, shopping for groceries or clothes, using the telephone, managing money, etc.

\*\*Self-care ADL refer to bathing, dressing and undressing, feeding self, using the toilet, taking medications, and not bedridden.

The Investigator (or designee) will make a determination of the relationship of the AE to the study drug using a 2-category system according to the following guidelines:

- **NOT RELATED** = The time course between the administration of investigational product and the occurrence or worsening of the AE rules out a causal relationship and another cause (eg, concomitant drugs, therapies, complications, comorbidities) is suspected;
- **RELATED** = The time course between administration of investigational product and the occurrence or worsening of the AE is consistent with a causal relationship and no other cause (eg, concomitant drugs, therapies, complications, comorbidities) can be identified.

An AE is associated with the use of the drug if there is a reasonable possibility that the experience may have been caused by the drug.

The action taken with the investigational product in response to the AE should be provided at the time the event is reported. For this study, options for action taken include the following:

- **Dosing stopped:** Medication administration was stopped before or during dosing.

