LOXO-292 was not mutagenic in the GLP bacterial mutation assay. LOXO-292 was not found to be phototoxic when evaluated in an in vitro neutral red uptake phototoxicity assay.

Based on preclinical pharmacology experiments with human cancer cells in vitro and in murine xenograft models, meaningful inhibition of RET in tumors is expected to be achievable with oral dosing regimens  $\geq$  40 mg/day.

Based on the nonclinical profile, including results from animal toxicology studies, theoretical risks of human exposure to LOXO-292 include the following: loss of appetite, decrease in body weight, increase in total white blood cells, neutrophils, and monocytes, decrease in albumin, increase in globulin, decreased albumin:globulin ratio, decrease in total protein, increased body temperature, lethargy, increase in cholesterol and triglycerides, increase in phosphorus, changes in taste sensation and/or development of xerostomia, GI symptoms/signs: nausea, vomiting, loose stools, abdominal discomfort, decreases in red cell mass (red blood cells, hemoglobin, hematocrit) and reticulocytes, decrease in platelets, increases in liver function tests (alkaline phosphatase [ALP], aspartate aminotransferase [AST], and alanine aminotransferase [ALT]).

LOXO-292 has been given orally and intravenously (IV) to mice, rats, dogs, minipigs, and monkey. LOXO-292 was absorbed and bioavailable in all species tested. Solubility studies and pharmacokinetic (PK) studies suggest that the PK exposure of LOXO-292 may be reduced by proton pump inhibitors and other antacids. LOXO-292 appears to be metabolized primarily by cytochrome P450 (CYP)3A4, but at therapeutically relevant exposures, it is not anticipated to inhibit or induce drug-metabolizing enzymes. LOXO-292 is also a substrate for breast cancer resistance protein transporter.

Refer to the IB for detailed background information on LOXO-292.

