### 6.5.1 Adverse Events

Adverse event definitions; assignment of severity, causality, action taken, and outcome; and procedures for reporting serious AEs (SAEs) are detailed in [Appendix C](#).

The condition of each subject will be monitored from time of signing the ICF to Clinic Discharge. In addition, subjects will be observed for any signs or symptoms and asked about their condition by open questioning, such as "How do you feel?" or "How have you been feeling since you were last asked?", as specified in [Table 6-1](#) and [Table 6-2](#), to assess for the occurrence of AEs. Subjects will also be encouraged to spontaneously report AEs occurring at any other time during the study.

All AEs, whether volunteered, identified by the subject's responses to How Do You Feel? inquiries, or noted on laboratory tests, vital signs measurements, ECGs, or physical examinations, will be recorded throughout the study (ie, from signing of the ICF until Study Completion), either as subject medical history (if the event is nonserious and reported prior to dosing) or as AEs (if serious or the event occurs after administration of LOXO-292). The nature, time of onset, duration, and severity will be documented, together with an Investigator's (or

designee's) opinion of the relationship to study drug. Adverse events recorded during the course of the study will be followed up, where possible, until they have resolved or become stable. This will be completed at the Investigator's (or designee's) discretion.

Subjects will receive a Safety Follow-up Call approximately 7 days after they are discharged from the CRU to determine if any AE has occurred since the last study visit.

At all times, a subject may be required to remain at the CRU for longer at the discretion of the Investigator (or designee).

Since the safety profile of LOXO-292 in humans has not been fully established, all SAEs related to LOXO-292 will be considered unexpected and reported as suspected unexpected serious adverse reactions.

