## **1.6 Reporting**

Food and Drug Administration-reportable AEs are AEs that are associated with the use of the drug and are serious and unexpected. Food and Drug Administration-reportable AEs will be reported by the Clinical Research Unit to the Sponsor, the Covance Medical Monitor, and the responsible Institutional Review Board (IRB).

Within 24 hours of when an AE that is potentially FDA-reportable is first recognized or reported, and within 24 hours of any SAE – either expedited or nonexpedited – being first recognized or reported, the Sponsor's Contact for Serious Adverse Event Reporting will be notified by the Investigator (or designee) in writing (eg, facsimile) using the following eFax number:

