**eFax: [contact]**

All SAEs occurring from the time of signing the Informed Consent Form through the Safety Follow-up Call must be reported. To report the SAE and/or potentially FDA-reportable AE, the completed SAE Report Form will be sent by eFax within 24 hours of first awareness. Incoming reports are reviewed during normal business hours. Additional reporting instructions and the SAE Report Form are provided in the Study Manual.

The Investigator (or designee) is not obligated to actively seek information regarding the occurrence of new SAEs beginning after the Safety Follow-up Call. However, if the Investigator (or designee) learns of such an SAE, and that event is deemed relevant to the use of study drug, he/she should promptly document and report the event. The Investigator (or designee) will be requested to supply detailed information as well as follow-up regarding the SAE.

The IRB will be notified of any FDA-reportable AE within the timeframe required by the IRB. The IRB Serious and Unexpected Adverse Experience Submission Form will be completed and submitted with the copy of the written confirmation or summary of the AE.

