10.5 Safety and Tolerability Assessments

10.5.1 Adverse Events

All AEs occurring during this clinical trial will be coded using the Medical Dictionary for Regulatory Activities (MedDRA®), Version 21.0. A treatment-emergent AE (TEAE) is defined as an AE that occurs postdose or that is present predose and becomes more severe postdose. The AE severity and relationship are determined by the investigator at the site. The severity grade of each AE will be based on the National Cancer Institute's Common Terminology Criteria for Adverse Events (CTCAE, Version 5.0) 5-point severity scale (Grade 1, 2, 3, 4 and 5). Not all grades are appropriate for all AEs. Therefore, some AEs are listed within the CTCAE with fewer than 5 options for grade selection.

All AEs captured in the database will be listed in by-subject data listings including verbatim term, coded term, part, severity grade, relationship to study treatment, outcome, and action; however, only treatment-emergent AEs (TEAEs) will be summarized. The frequency of TEAEs (the number of TEAEs, the number of subjects experiencing a TEAE, and the percentage of subjects experiencing a TEAE) will be summarized by part, treatment, and by system organ class and preferred term. The summary and frequency TEAE tables will be presented for all causalities and for those TEAEs considered related to the study treatment (those that have a relationship of related). Any life-threatening or serious AEs will be tabulated. For any AEs that change severity ratings the AE will be included only once under the maximum severity rating in the summaries.

For orally administered LOXO-292 and [¹⁴C]-LOXO-292, onset times postdose are calculated from the time of dose administration (Parts 1 and 2).

For [¹⁴C]-LOXO-292 administered as an IV push, onset times postdose are calculated from the start of infusion (Part 2 only).

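### The two adverse-event causality categories leave mixed-cause events unclassified, and RELATED is stricter than the protocol's own reasonable-possibility standard

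*Protocol*

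**What the plan says.** Protocol Appendix C 1.2 has the investigator choose between two categories, offered as guidelines.

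- NOT RELATED: the time course "rules out a causal relationship and another cause (eg, concomitant drugs, therapies, complications, comorbidities) is suspected".
- RELATED: the time course "is consistent with a causal relationship and no other cause (eg, concomitant drugs, therapies, complications, comorbidities) can be identified".

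The sentence after these definitions introduces another term and another test. An adverse event "is associated with the use of the drug if there is a reasonable possibility that the experience may have been caused by the drug".

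The two terms are then used in different places:

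- Appendix C 1.6 defines FDA-reportable events with the second term: "reportable AEs are AEs that are associated with the use of the drug and are serious and unexpected".
- Protocol 6.5.1 uses the first: "all SAEs related to LOXO-292 will be considered unexpected and reported as suspected unexpected serious adverse reactions".
- SAP 10.5.1 leaves relationship to the investigator, gives no definition of its own, and plans TEAE tables for all causalities and "for those TEAEs considered related to the study treatment (those that have a relationship of related").

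Separately from causality, Appendix C 1.6 states: "All SAEs occurring from the time of signing the Informed Consent Form through the Safety Follow-up Call must be reported".

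**The concern.** A two-category scale should place every event in exactly one category. Here both definitions are conjunctions and they are not complements of each other. The event left out is the ordinary hard case: onset fits the drug, but something else could also explain it. Followed literally, the guidance bars that event from RELATED, even where the next sentence would call it associated with the drug.

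What is exposed is the related-TEAE summary, which is the planned statement of drug-attributed tolerability. It copies the investigator's field with no further rule, so any inconsistency in coding passes straight into the table.

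**Working it through.** The plan states no figure on this point. The check is logical, followed by a little arithmetic on foreseeability and size.

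**1. Enumerate the definitions.** Cross time course with other cause, using the conditions in Appendix C 1.2.

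| Time course | Other cause | Category |
|---|---|---|
| Ruled out | Present | NOT RELATED |
| Ruled out | Absent | none |
| Consistent | Absent | RELATED |
| Consistent | Present | none |

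Two of four combinations are classified. The second row is a technicality and nothing here relies on it. The fourth row matters.

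**2. Allow for the difference in wording.** NOT RELATED speaks of a *suspected* cause and RELATED of an *identified* one. Split other cause into three levels:

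| Time course | None | Suspected, not identified | Identified |
|---|---|---|---|
| Ruled out | none | NOT RELATED | NOT RELATED |
| Consistent | RELATED | RELATED | none |

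Four of six combinations are classified. The combination of consistent timing and an identified other cause is still unassigned, so the gap does not depend on how the words are read.

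**3. Compare with the next sentence.** An event with consistent timing and an identified other cause fails RELATED, because another cause has been identified. It can still be a reasonable possibility that the drug caused it. RELATED is therefore the stricter test.

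**4. Look for a default.** Protocol 6.5.1, Appendix C 1.1, 1.2 and 1.6, and SAP 10.5.1 contain none, and none of them links *related* to *associated*.

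**5. Are such events foreseeable?**

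- Protocol 2.2 lists among the theoretical drug risks "nausea, vomiting, loose stools, abdominal discomfort, decreases in red cell mass".
- Protocol 2.3 reports diarrhea in 16% of 57 patients: 0.16 × 57 = 9.1, about 9. These were patients with advanced tumors on dosing up to 160 mg BID, so this is not a rate for healthy volunteers given one dose.
- Competing causes are built into the design. Protocol 6.3.1 puts confined subjects on a high-fiber diet with prunes as needed. Protocol 6.3.2 permits acetaminophen with approval.
- Appendix B gives the maximum blood draw. Part 1: 4 + 16 + 16 + 150 + 190 = 376 mL. Part 2: 4 + 16 + 16 + 150 = 186 mL. The Part 1 maximum assumes confinement to Day 22, and both totals include samples taken before dosing.

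This shows only that mixed-cause events can be expected to arise. It gives no count.

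**6. Size in the table.** Six subjects are planned per part (Protocol 5). If six are dosed, and one subject enters or leaves a related-TEAE row because of one such event, the percentage moves by 1/6 = 16.7 points.

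**The case against.** **Guidelines only.** The definitions are guidance for a judgement, and Protocol 6.5.1 records the investigator's opinion. A choice between two boxes will always be made, and the documents describe a single clinical research unit, so variation between sites is not an issue. This is right, and it limits the effect. But the guidance gives no answer exactly where judgement is needed, and similar events can still be coded differently within one unit.

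**No contradiction.** The reasonable-possibility sentence may be the overarching standard, which would settle the mixed-cause case, or it may be a separate definition for FDA reporting, since Appendix C 1.6 uses the same phrase. Either reading is tenable. The text does not choose, and the choice changes how the mixed-cause event is coded.

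**Direction unproven.** NOT RELATED is also strict, because timing must exclude causality. An investigator could as easily resolve the gap towards RELATED and over-count. This stands: under-counting follows only if RELATED is applied to the letter and the remainder falls to NOT RELATED.

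**Weak foreseeability.** The subjects are healthy, medications are restricted, the listed risks are theoretical, and laboratory changes become adverse events only if judged clinically relevant. These points limit the expected number of events. They do not close the gap.

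**Small consequence.** All-causality tables and by-subject listings showing relationship are planned, so a reader can re-examine each attribution. This also stands, and it is why the point is not a critical one.

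**Conclusion.** The concern holds. On the protocol's wording, an event with compatible timing and another identifiable cause belongs to neither category, and RELATED is narrower than the reasonable-possibility standard beside it.

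The exposed output is the related-TEAE table, which may be inconsistently classified or under-counted against that standard. The number of affected events and the direction of any error cannot be derived from the documents. The 16.7-point shift assumes six dosed subjects and one reclassified subject.

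No loss of reportable serious events is shown. Appendix C 1.6 uses the looser term and requires every SAE to be sent to the sponsor. For SAEs, what remains is a mismatch of terms between that section and Protocol 6.5.1. The wording should be corrected, but the primary objectives and the all-causality safety outputs are unaffected.

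**What to change.** In Appendix C 1.2, define RELATED as a reasonable possibility that the study drug caused the event, whether or not another cause is present, and NOT RELATED as all other events. The categories are then complementary, under a standard the protocol already contains.

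Use that single defined term in Protocol 6.5.1, Appendix C 1.2 and 1.6, and SAP 10.5.1, with the SAP citing the protocol definition. Leave the notification of all SAEs, which does not depend on causality, as it is.

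The cost is wording in the protocol and the eCRF completion guideline, plus one cross-reference in the SAP. No new data are needed, though any relationship already recorded should be checked against the new definition. The related-event rate may look slightly less favourable if mixed-cause events would otherwise have been coded NOT RELATED.
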